##### ***Analysis of all treatment-emergent adverse events***

The following treatment-emergent adverse event summaries will be generated for the safety population.

- Overview of treatment-emergent adverse events, summarizing number (%) of patients with any
  - Treatment-emergent adverse event
  - Serious treatment-emergent adverse event
  - Treatment-emergent adverse event leading to death
  - Treatment-emergent adverse event leading to permanent treatment discontinuation
- All treatment-emergent adverse event by primary SOC, HLGT, HLT, and PT, showing number (%) of patients with at least 1 treatment-emergent adverse event sorted by the SOC

internationally agreed order. The other levels (HLGT, HLT, PT) will be presented in alphabetical order

- All treatment-emergent adverse events by primary SOC and PT, showing the number (%) of patients with at least 1 treatment-emergent adverse event, sorted by the internationally agreed SOC order and by decreasing incidence of PTs within each SOC. This sorting order will be applied to all other tables, unless otherwise specified
- All treatment-emergent adverse events regardless of relationship and related by primary SOC, HLGT, HLT and PT, showing the number (%) of patients with at least 1 treatment-emergent adverse event, sorted by the internationally agreed SOC order. The other levels (HLGT, HLT, PT) will be presented in alphabetical order

All treatment-emergent adverse events by maximal severity, presented by primary SOC and PT, showing the number (%) of patients with at least 1 treatment-emergent adverse event by severity (ie, mild, moderate, or severe), sorted by the sorting order defined above

#### ***Analysis of all treatment emergent serious adverse event(s)***

- All treatment-emergent serious adverse events by primary SOC, HLGT, HLT, and PT, showing the number (%) of patients with at least 1 serious treatment-emergent adverse event, sorted by the internationally agreed SOC order. The other levels (HLGT, HLT, PT) will be presented in alphabetical order
- All treatment-emergent serious adverse events by primary SOC and PT, showing the number (%) of patients with at least 1 treatment-emergent adverse event, sorted by the internationally agreed SOC order and by decreasing incidence of PTs within each SOC. This sorting order will be applied to all other tables, unless otherwise specified
- All treatment-emergent serious adverse events regardless of relationship and related to IMP, by primary SOC, HLGT, HLT, and PT, showing the number (%) of patients with at least 1 treatment-emergent serious adverse event, sorted by the internationally agreed SOC order. The other levels (HLGT, HLT, PT) will be presented in alphabetical order
- The event rate per patient-year (the number of events in question divided by total treatment exposure in patient years) will be provided for SAEs by SOC and PT
- By-patient listing of treatment-emergent SAEs showing analysis group (IAT vs DAT), patient ID, time since first dose of Alemtuzumab infusion in years, age, gender, race, primary SOC decode, PT decode, verbatim (diagnosis), onset date and study day, date of death (if relevant), recovery date/time, event duration, outcome, intensity/grade, relationship to study treatment, action taken with study treatment AE serious criteria.

#### ***Analysis of all treatment-emergent adverse event(s) leading to treatment discontinuation***

- All treatment-emergent adverse events leading to treatment discontinuation by primary SOC, HLGT, HLT, and PT, showing the number (%) of patients sorted by the internationally agreed SOC order. The other levels (HLGT, HLT, PT) will be presented in alphabetical order

- All treatment-emergent adverse events leading to treatment discontinuation by primary SOC and PT, showing the number (%) of patients with at least 1 treatment-emergent adverse event, sorted by the internationally agreed SOC order and by decreasing incidence of PTs within each SOC. This sorting order will be applied to all other tables, unless otherwise specified
- By-patient listing of treatment-emergent adverse events leading to treatment discontinuation showing analysis group (IAT vs DAT), patient ID, time since first dose of Alemtuzumab infusion in years, age, gender, race, primary SOC decode, PT decode, verbatim (diagnosis), onset date and study day, date of death (if relevant), recovery date/time, event duration, outcome, intensity/grade, relationship to study treatment, action taken with study treatment AE serious criteria.

### ***Analysis of adverse events of special interest (AESI)***

- All treatment-emergent adverse events of special interest by primary SOC, HLG, HLT, and PT, showing the number (%) of patients sorted by the internationally agreed SOC order. The other levels (HLG, HLT, PT) will be presented in alphabetical order
- All treatment-emergent adverse events of special interest by primary SOC and PT, showing the number (%) of patients with at least 1 treatment-emergent adverse event, sorted by the internationally agreed SOC order and by decreasing incidence of PTs within each SOC. This sorting order will be applied to all other tables, unless otherwise specified
- All treatment emergent adverse events of special interest by PT, showing the number (%) of patients, sorted by decreasing incidence of PT
- The event rate per patient-year (the number of events in question divided by total treatment exposure in patient years) for non-temporary AESI(s) will be provided by SOC and PT
- The frequency of treatment-emergent adverse events over time will be provided for the non-temporary treatment-emergent AESIs, where the time intervals will be defined as: <2 courses, 2 – 4 courses, 4 – 6 courses, 6 – 8 courses, etc. In each time interval, the denominator for calculation of percentage will be the number of patients who entered the time interval and the numerator will be the number of patients with at least 1 treatment emergent AESI occurring in this time interval. Note that only the first event will be counted and all recurrent events will not be included
- For retreated population, the frequency of treatment-emergent temporary adverse events over time will be provided for the temporally associated AESIs (pulmonary alveolar hemorrhage, myocardial ischemia, myocardial infarction, stroke, cervicocephalic arterial dissection), where the time intervals will be defined as: during alemtuzumab infusion day 1, during alemtuzumab infusion day 2, during alemtuzumab infusion day 3, 1 day after alemtuzumab infusion, 2 days after alemtuzumab infusion and 3 days after alemtuzumab infusion. In each time interval, the denominator for calculation of percentage will be the number of patients who entered the time interval and the numerator will be the number of patients with at least 1 treatment emergent AESI occurring in this time interval. Note that only the first event will be counted and all recurrent events will not be included

- By-patient listing of treatment-emergent adverse events of special interest showing analysis group (IAT vs DAT), patient ID, number of alemtuzumab courses age, gender, race, AESI group, primary SOC decode, PT decode, verbatim (diagnosis), onset date and study day, date of death (if relevant), recovery date/time, event duration, outcome, intensity/grade, relationship to study treatment, action taken with study treatment AE serious criteria.

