## **6.2 DURATION OF STUDY PARTICIPATION**

### **6.2.1 Duration of study participation**

Study duration will be 5 years (plus a window of 6 months) from the day of the enrollment of the first patient.

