#### 8.1.1 Administration

There is no fixed treatment requirement or schedule. Administration of alemtuzumab will only be done following a decision from the Study Investigator that an additional “as needed” course is indicated.

Alemtuzumab will be then administered by IV infusions in a supervised medical setting at a dose of 12 mg/day on 3 consecutive days (36 mg total dose) at least 12 months after the prior treatment course.

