#### **2.4.5 Analyses of safety data**

The summary of safety results will be presented in overall group and by subgroups (IAT vs DAT).

Only data collected in TOPAZ study will be used for analysis in addition of baseline information from previous studies.

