#### **General common rules**

All safety analyses will be performed on the safety population as defined in [Section 2.3.1.1](#), unless otherwise specified, using the following common rules:

- The baseline value is defined as the available value assessed on or prior to the V01 Selection visit, unless otherwise specified. If laboratory, vital sign and physical examinations were performed in CAMMS03409 study within the pre-specified time-windows, then the last assessment within the time-window can be considered as baseline when the corresponding V01 assessments are missing.
- The potentially clinically significant abnormality (PCSA) values are defined as abnormal values considered medically important by the Sponsor according to predefined criteria/thresholds based on literature review and defined by the Sponsor for clinical laboratory tests and vital signs (PCSA version dated May 2014 [[Appendix A](#)])
- PCSA criteria will determine which patients had at least 1 PCSA during the treatment-emergent adverse event period, taking into account all evaluations performed during the treatment-emergent adverse event period, including nonscheduled or repeated evaluations.

The number of all such patients will be the numerator for the on-treatment PCSA percentage

- The treatment-emergent PCSA denominator by group for a given parameter will be based on the number of patients assessed for that given parameter in the treatment-emergent adverse event period in overall group and by subgroups (IAT vs DAT) on the safety population.
- For quantitative safety parameters based on central laboratory/reading measurements, descriptive statistics will be used to summarize results and change from baseline values by visit and analysis group.
- The analysis of the safety variables will be essentially descriptive and no systematic testing is planned.

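### AESI percentages by number of courses ignore time at risk, so they are not comparable between course intervals; by-course relapse summaries group patients partly by the outcome

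*SAP*

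**What the plan says.** **AESI table.** In SAP 2.4.5.1 (Analysis of adverse events of special interest), the frequency of non-temporary AESIs over time is tabulated in intervals whose unit is courses: "where the time intervals will be defined as: <2 courses, 2 – 4 courses, 4 – 6 courses, 6 – 8 courses, etc". For each interval, "the denominator for calculation of percentage will be the number of patients who entered the time interval"; the numerator is patients with at least one AESI in it. A note adds: "Note that only the first event will be counted and all recurrent events will not be included". The same section plans an event rate per patient-year, but this "for non-temporary AESI(s) will be provided by SOC and PT", not by course interval.

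SAP 2.4.5 limits the safety data: "Only data collected in TOPAZ study will be used for analysis in addition of baseline information from previous studies". On retreatment, Protocol 8.1.1 states: "There is no fixed treatment requirement or schedule". It sets a minimum of 12 months between courses and no maximum.

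**Relapse summaries.** SAP 2.4.4 also plans results by total number of alemtuzumab courses (≤3 vs >3). SAP 2.4.4.1.1 and 2.4.4.1.2 apply the by-course view to the annualized relapse rate (ARR) and to the relapse-free Kaplan-Meier graph, with relapses counted from the start of CAMMS323/324. Protocol section 4 says retreatment in CAMMS03409 could be offered on documented resumed disease activity. Protocol 6.1 gives clinical and/or imaging activity as the example of a factor behind a TOPAZ treatment decision.

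**The concern.** A percentage of patients who entered an interval measures risk only if time in the interval is similar across intervals. Here an interval is as long as the investigator's decisions and the TOPAZ window make it. A patient may sit in one interval for all of TOPAZ or reach the next one shortly before the end. A constant yearly risk can then look as if it falls or rises with more courses.

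Two rules are also missing. The values 4 and 6 each end one interval and start the next, and the SAP does not place a patient with exactly 4 courses. It also does not say whether patients who had the same AESI before TOPAZ stay in the denominator.

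This matters because long-term safety is the primary objective, and Protocol section 4 says that the benefits and risks of more than two courses are not fully established. A reader would turn to this table for that question. An artificial fall would reassure falsely, and an artificial rise would alarm falsely.

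The relapse split has a different weakness. A relapse counted in the outcome can prompt the course that moves the patient into the >3 group.

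**Working it through.** The documents give no AESI or relapse rate by course and no course distribution at TOPAZ entry, so there is no planned figure to reproduce. All rates below are assumptions.

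**1. Time in the interval.** With constant hazard h over T years, the percentage with an event is 1 − exp(−hT).
- h = 0.05, T = 5: 1 − exp(−0.25) = 22.1%.
- h = 0.05, T = 2: 1 − exp(−0.10) = 9.5%.
- h = 0.02: 9.5% and 3.9% for the same two times.

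**2. The planned percentage under constant risk.** Simulation of 60,000 patients per run: hazard 0.05 per year with no effect of courses; last course 1-5 years before D1; follow-up 3.5-5 years; further courses at least 12 months apart at 0.05, 0.1, 0.2 or 0.4 per year. The table gives the ratio of the planned percentage, 4-5 vs 2-3 courses.

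| Courses at entry (% of patients) | Enter with 2-3 | 0.05 | 0.1 | 0.2 | 0.4 |
|---|---|---|---|---|---|
| A: 2 (60), 3 (25), 4 (10), 5 (5) | 85% | 0.86 | 0.81 | 0.72 | 0.66 |
| B: 1 (5), 2 (55), 3 (25), 4 (10), 5 (5) | 80% | 0.89 | 0.81 | 0.72 | 0.69 |
| C: 2 (40), 3 (25), 4 (25), 5 (10) | 65% | 0.90 | 0.89 | 0.84 | 0.85 |
| D: 2 (10), 3 (40), 4 (45), 5 (5) | 50% | 1.00 | 0.99 | 1.10 | 1.31 |
| E: 2 (75), 3 (23), 4 (2) | 98% | 0.63 | 0.57 | 0.54 | 0.59 |

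The person-year rate was 0.048-0.052 in both intervals in all 20 runs.

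A simulation of different structure agrees. It covers 11 years, gives extra courses only after a relapse, and takes TOPAZ as years 6 to 11. With half-open intervals starting at 2, 4 and 6 courses, the percentages were 19.3, 14.2 and 8.5 over mean times of 4.33, 3.11 and 1.82 years. Dividing gives 19.3/4.33 = 4.46, 14.2/3.11 = 4.57 and 8.5/1.82 = 4.67 per 100 person-years, which is nearly flat.

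**3. The boundary.** In mix D at 0.4 courses per year, placing exactly 4 in the upper interval gives 10.7% then 14.0%, a rise. Placing it in the lower gives 13.5% then 10.3%, a fall. Mix D at 0.2 also reverses (1.10 vs 0.69). At 0.05 and 0.1 it shows no rise to reverse, and mix A falls under both placements.

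**4. Is a plain person-year rate enough?** Let risk be 0.05 per year until 48 months after the last course and 0.01 after, again with no effect of course number. At 0.05-0.2 courses per year the unsplit rate ratio, 4-5 vs 2-3, was 1.02-1.78. In mix A at 0.05 per year, for example, it was 0.027/0.023 = 1.17. In runs extended to 0.4 per year, mixes A, B, C and E gave rate ratios of 1.05-1.81 against percentage ratios of 0.78-1.11. The percentage was closer to 1 in 15 of those 16 runs. In mix D both misled (percentage 1.12-1.83, rate 1.12-1.44). Split at 48 months, the rates for 2-3 and 4-5 courses agreed: 0.048-0.051 vs 0.048-0.052 before, and 0.010-0.011 vs 0.009-0.012 after.

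**5. Relapse.** Simulation of 30,000 patients per run: 6 years before TOPAZ plus 3.5-5 in it, two initial courses, one common relapse rate (0.12-0.25 per year), and 0.05-0.10 other courses per year. When 30-60% of relapses trigger a course, the ARR ratio >3 vs ≤3 is 1.35-2.11. When none does, it is 0.97-1.03. In one run (rate 0.18, 30% triggering), 6.9% of the >3 group and 19.8% of the ≤3 group were relapse-free at 9.5 years.

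**The case against.** The strongest reply is that these are supplementary displays. The SAP says: "The analysis of the safety variables will be essentially descriptive and no systematic testing is planned". IAT versus DAT is the main efficacy analysis, patient-year AESI rates are already planned, and the by-patient AESI listing shows number of courses. All the sizes above come from assumed inputs. This limits the weight of the point but does not remove it: the patient-year rates are not by course, and the listing covers only patients with events, so by-course person-time cannot be rebuilt from either.

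A second reply is that person-years are no cure. That stands for an unsplit rate (step 4). The percentage often looked better there only because two biases cancelled, which does not validate it.

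Several stronger readings are tempting and not supported:
- *The intervals overlap and patients are counted twice.* The opening category below 2 fits half-open intervals. What is missing is a stated rule.
- *The table will show falling risk.* The direction depends on an entry distribution that the documents do not give.
- *Late enrolment biases the intervals.* Protocol 6.2.1 says: "Study duration will be 5 years (plus a window of 6 months) from the day of the enrollment of the first patient". Later enrollees do have less follow-up, but this distorts the comparison only if enrolment date is related to course count, which nothing shows.
- *Earlier AESIs distort the gradient.* Keeping those patients in the denominator lowers percentages. If the proportion is the same in every interval, the ratios do not change.
- *The SAP plans a by-course hazard ratio for relapse.* None is explicitly specified; SAP 2.4.4 says that by-course results are summarized. The ARR is also shown by year, which helps a reader see when relapses occurred.
- *The relapse calculation carries over to EDSS and MRI.* SAP 2.4.4 restricts those outcomes to TOPAZ data plus baseline, so it does not carry over directly.

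**Conclusion.** The AESI concern holds. As defined, the percentages are not comparable between course intervals, and no planned output supplies person-time by course. Under constant risk the distortion ran from about half (0.54) to about a third too high (1.31) across the assumed mixes, and the boundary choice reversed the direction in some of them. The real size and direction are unknown.

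The relapse concern holds in a narrower form. Disease activity is one ground for retreatment, alongside imaging activity and investigator discretion, so relapses help decide the group without fully determining it. As description the split is acceptable. It does not estimate an effect of retreatment.

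This should be corrected before the tables are programmed. It does not affect the main efficacy analysis or the overall AESI summaries.

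**What to change.** **AESI table (SAP 2.4.5.1).**
- Define non-overlapping intervals of courses received to date: 0-1, 2-3, 4-5 and ≥6, updated at each new course.
- Beside the planned percentage, report first TOPAZ-onset events, TOPAZ person-years at risk and the rate with 95% CI. Person-years run from the later of D1 and the start of the interval to the earliest of first event, next interval or end of participation. The person-years in SAP 2.4.3.1 start at first treatment in the prior studies and do not match TOPAZ-only events.
- Split the person-years at 48 months after the last infusion, the documents' own monitoring period (Protocol 9.5.2.1 and 10.1.6.2). The split is required. Pool sparse top intervals.
- State whether patients with the same AESI before TOPAZ are in the risk set.
- Footnote that differences between intervals may also reflect selection for retreatment.

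**By-course efficacy (SAP 2.4.4 to 2.4.4.1.5).** Keep the ≤3 vs >3 relapse summaries, including the Kaplan-Meier graph, as description. Add no by-course hazard ratio or model-based comparison of relapse. Footnote all by-course efficacy results: additional courses follow disease activity, so group differences do not estimate an effect of retreatment.

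**Cost.** SAP wording and one course-interval data set, with no new data. The table becomes less simple, and confidence intervals will be wide in sparse rows.

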# 1 FLOW CHARTS

## 1.1 GRAPHICAL STUDY DESIGN

- ★ Only for patients treated with alemtuzumab: monthly laboratory safety variables collection for 48 months after last infusion
  - For patients who received alemtuzumab in CAMMS03409 study less than 48 months before entering in LPS13649 study, and
  - For patients receiving retreatment with alemtuzumab during the LPS13649 study

\* After completion of 5 years of the first patient inclusion, the next scheduled visit for any patient will be performed as EOS visit.

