- During infusion: continuous or hourly monitoring BP/HR; intermittently ambulation, compressive stocking.
- Post infusion: inform/remind patient any abnormal clinical sign/symptoms related to infusion.
- Periodic liver function test.

Please refer to [Section 10.1.6](#) for details.

Study CAMMS03409 is an open-label extension study designed to provide additional safety monitoring for up to 60 months, and as-needed alemtuzumab retreatment to qualifying patients who received alemtuzumab in prior Genzyme-sponsored studies CAMMS223, CAMMS323 and CAMMS324. In addition, patients who received SC IFNB-1a in the earlier studies had the opportunity to receive 2 annual courses of alemtuzumab, and possibly subsequent as-needed alemtuzumab retreatment.

In CAMMS03409, “as needed” retreatment with alemtuzumab could be offered to patients upon documented evidence of resumed MS disease activity, subject to safety-related disqualifications. The additional course(s) of alemtuzumab were administered at 12 mg/day on 3 consecutive days (36 mg total dose) at least 12 months after the prior treatment course. The benefits and risks of >2 treatment courses have not been fully established, but results suggest that the safety profile does not appear to change with additional courses.

The present study LPS13649 will provide long term safety and efficacy data on the patients who completed the extension study CAMMS03409, as well as on additional as-needed alemtuzumab retreatment. In addition, the study will provide information about the safety profile of patients who received other commercial DMTs following alemtuzumab treatment.

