### **5.2 SECONDARY**

The secondary objectives are:

- To evaluate long term efficacy of alemtuzumab.
- To evaluate the safety profile of patients who received other DMT following alemtuzumab treatment.
- To evaluate patient-reported quality of life (QoL) outcomes and health resource utilization of patients who received alemtuzumab.
- To evaluate as needed re-treatment with alemtuzumab and other DMTs.

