### **6.2.2 Determination of end of clinical trial (all patients)**

The end of the clinical trial occurs 5 years (plus a window of 6 months) after the inclusion of the first patient.

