#### **10.1.6.2 Post-alemtuzumab treatment monitoring**

The following parameters must be obtained at monthly intervals ( $\pm 3$  days) until 48 months after the last infusion of alemtuzumab:

- CBC with differential (including platelet count).
- Serum creatinine.
- Liver function test (ALT, AST, ALP, albumin, total protein, direct and total bilirubin)
- Urinalysis (minimally including determination of urine protein and red blood cells) with microscopy (if not performed in the previous 2 weeks). (Please also refer to footnote in [Section 9.5.2](#)).

TSH must be obtained every 3 months ( $\pm 3$  days) until 48 months after the last infusion of alemtuzumab.

For women, an HPV screening must be performed every 12 months ( $\pm 14$  days) until 48 months safety FU is completed.

The blood and urine sampling will be performed in local laboratories at the patients' convenience. Results must be sent to the Study Investigator. The Study Investigator must review laboratory data as soon as the results are available and they will be recorded in the e-CRF.

If the 48-month period of safety follow-up continues after the study ends, the patient will be followed by their physician in a regular healthcare setting, in line with the local approved Risk Minimization Plan for alemtuzumab, until the 48-month period is completed.

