#### **2.4.5.1 Analyses of adverse events**

##### ***Generalities***

All the reported AE will be considered as treatment emergent adverse event (TEAE).

Adverse event incidence tables will present by SOC, HLGT, HLT, and PT, sorted in alphabetical order in overall group and by subgroups (IAT vs DAT), the number (n) and percentage (%) of patients experiencing an adverse event. Multiple occurrences of the same event in the same patient will be counted only once in the tables. The denominator for computation of percentages is the safety population in overall group and by subgroups (IAT vs DAT).

Sorting within tables ensures the same presentation for the set of all adverse events within the observation period. For that purpose, the table of all treatment-emergent adverse events presented by SOC and PT sorted by the internationally agreed SOC order and decreasing frequency of PTs in overall group within SOCs will define the presentation order for all other tables unless otherwise specified.

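### No adverse-event table isolates SAEs or delayed AESIs after a TOPAZ re-treatment, and a last infusion after calendar month 12 to 18 cannot have 48 months observed in the study

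*SAP*

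**What the plan says.** SAP 2.3.1.1 defines a retreated population: safety patients dosed in TOPAZ. Among adverse-event outputs it is used twice. Infusion-associated reactions are analysed separately for it (SAP 2.1.4.1 and 2.4.5.1). The AESI part of 2.4.5.1 then states: "For retreated population, the frequency of treatment-emergent temporary adverse events over time will be provided for the temporally associated AESIs", with intervals for infusion days 1 to 3 and for 1, 2 and 3 days afterwards.

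The other tables of adverse events, SAEs and AESIs use the safety population, overall and by IAT/DAT. Non-temporary AESIs are also shown by number of courses (<2, 2–4, 4–6, 6–8 and so on) and as events per patient-year. SAEs also get a patient-year rate.

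Other data are separated for retreated patients: laboratory variables with a baseline before the first TOPAZ dose (2.4.5.3), in monthly windows (TSH every 3 months) over 48 months after the last infusion (2.5.3.1); vital signs (2.4.5.4); and an ECG listing (2.4.5.5).

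Protocol 5.2 lists as a secondary objective "To evaluate as needed re-treatment with alemtuzumab and other DMTs". Protocol 6.1 requires 48 months of follow-up after the last infusion. Protocol 6.2.2 sets a calendar end: "The end of the clinical trial occurs 5 years (plus a window of 6 months) after the inclusion of the first patient". Protocol 1.1 adds: "After completion of 5 years of the first patient inclusion, the next scheduled visit for any patient will be performed as EOS visit". What remains leaves the study: "If the 48-month period of safety follow-up continues after the study ends, the patient will be followed by their physician in a regular healthcare setting" (Protocol 10.1.6.2).

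**The concern.** The protocol asks for 48 months of monitoring after a course because important harms, autoimmunity among them, can appear late. Yet the adverse-event tables specific to re-treatment stop 3 days after infusion. Beyond that, events before a TOPAZ infusion, events after it, and events in patients never re-infused are counted together. If re-treatment added delayed risk, the pooled percentage would show that excess shrunk by a factor equal to the re-treated share of patients.

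The calendar end adds a second problem. A crude percentage of retreated patients with an event would mix people watched for 48 months with people watched for far less, and short follow-up makes re-treatment look safer. The plan does not say how the truncated window is handled in adverse-event tables. At stake is what the report can say on the re-treatment objective. Protocol section 4 notes: "The benefits and risks of >2 treatment courses have not been fully established".

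**Working it through.** The plan states no sample size, power or precision figure, so there is none to reproduce. The check has two parts.

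**1. Does any planned adverse-event output isolate time after a TOPAZ infusion?**

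- *Course bands (SAP 2.4.5.1).* These count courses, not time. A patient who enters with 2 courses and receives a third stays in the 2–4 band before and after the infusion. Some re-treatments do cross a band (1 to 2, for example), but the bands share endpoints, so a patient with 4 courses fits two of them.
- *Patient-year rates.* The SAP's only person-year definition (2.4.3.1) runs from first treatment in the prior studies to the end of TOPAZ. SAP 2.4.5 counts TOPAZ events only. Neither numerator nor denominator starts at the re-treatment.
- *Listings.* The SAE listing gives time since the first alemtuzumab dose. The AESI listing gives number of courses and onset date. Neither gives time since the last infusion.
- *Laboratory tables.* These are separated for retreated patients and bear on ITP, nephropathy, hepatitis and thyroid disease. They are test values, not diagnoses, and cannot show malignancy, PML, pneumonitis or most serious infections. The Kaplan-Meier analysis there covers liver tests only.

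None does.

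**2. How much of the 48 months can be observed?**

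Inputs: study end T = 60 to 66 months after first enrolment (Protocol 6.2); window 48 months (Protocol 6.1). For a last infusion at calendar month t:

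- observed follow-up = min(48, T − t)
- full observation needs t ≤ T − 48: 60 − 48 = 12, or 66 − 48 = 18

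That much follows from the documents. The share affected needs assumptions, because the documents give neither re-treatment timing nor the enrolment period. I take one TOPAZ course per re-treated patient.

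Even timing, everyone enrolled on day 0:

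- truncated share = 48/T: 48/60 = 80%; 48/66 = 72.7%
- mean observed = [(T − 48) × 48 + 48²/2]/T: (576 + 1152)/60 = 28.8 months; (864 + 1152)/66 = 30.5 months

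Early timing: exponential with median m months after entry, restricted to infusions before T. With no spread of entry,

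- truncated share = [2^(−(T−48)/m) − 2^(−T/m)] / [1 − 2^(−T/m)]
- m = 12, T = 60: (0.5 − 0.03125)/0.96875 = 48.4%
- m = 6, T = 66: (0.125 − 0.00049)/0.99951 = 12.5% (12.4% simulated)

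The staggered-entry results, with entry uniform over 12 or 24 months, were simulated with 1,000,000 draws. Percentage truncated:

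| Timing (assumed) | T = 60, entry over 0 / 12 / 24 months | T = 66, entry over 0 / 12 / 24 months |
|---|---|---|
| Even | 80.0 / 89.2 / 94.6 | 72.7 / 80.3 / 88.7 |
| Median 24 months | 64.4 / 80.4 / 89.6 | 52.4 / 64.8 / 78.9 |
| Median 18 months | 58.9 / 77.1 / 88.1 | 45.8 / 59.5 / 75.9 |
| Median 12 months | 48.4 / 70.8 / 85.0 | 33.9 / 49.4 / 70.2 |
| Median 6 months | 24.9 / 54.0 / 76.9 | 12.4 / 27.1 / 56.5 |

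A further TOPAZ course moves the last infusion later and restarts the 48 months.

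**The case against.** The strongest reply is that the SAP does follow retreated patients for delayed harm. Its laboratory analysis spans the 48 months with a pre-infusion baseline and covers the tests used to monitor for most of the autoimmune conditions. This stands: a reader might infer that delayed risk in retreated patients is ignored, and the documents do not support that. The gap is in tables of diagnosed events.

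The near-infusion tables are also justified. Protocol section 4 names infusion reactions and serious infections beside autoimmunity, and describes stroke, infarction and dissection within three days.

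The protocol's sentence on more than 2 courses goes on to say that results so far suggest no change in the safety profile. It does not single out delayed autoimmunity as the open question, and should not be cited as if it did.

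The truncation is openly stated. Related SAEs remain reportable after a patient's study end (Protocol 10.4.3). Protocol 11.2 asks for time to treatment, and the laboratory tables give numbers at each assessment, so observed time is partly visible. None of this supplies an event rate or a censoring rule.

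A reader might also infer from SAP 2.4.5, which cites Section 2.3.1.1 for the safety population, that every safety table is on the retreated population, since that is the heading of 2.3.1.1. The wording says safety population throughout, and 2.4.5.3 and 2.4.5.4 name the retreated population where it is meant. The number looks like a slip for 2.3.1.

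Finally, re-treatment is the investigator's choice in a non-comparative study, so any contrast with time not re-treated is confounded. This stands and limits the fix to description.

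**Conclusion.** The point holds for adverse-event tables. As planned, SAEs and non-temporary AESIs after a TOPAZ infusion cannot be read from any table, and the laboratory, vital-sign and ECG outputs do not replace them. The limit at calendar month 12 to 18 rests only on the documents' own figures.

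The share of retreated patients affected is not a document fact. It is 73–95% under even timing and 12–85% with a median of 6 or 12 months after entry; medians of 18 or 24 months give 46–90%. A reader might infer that most retreated patients are truncated. That is plausible, but it fails if re-treatment came early and enrolment was quick. Nor can the documents bear the claim that the plan says nothing on re-treatment safety: course bands, listings and laboratory tables each give part of it. The gap weakens the answer to a stated secondary objective without invalidating the other safety outputs. It should be closed.

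**What to change.** In SAP 2.4.5.1 add descriptive tables for the retreated population:

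- SAEs and non-temporary AESIs with onset from the first TOPAZ infusion, as rates per person-year of observed time from that infusion to the earlier of 48 months after the last infusion and the patient's end of study.
- Cumulative incidence of the same events by time since infusion, with numbers at risk and censoring at end of study. State whether the clock restarts at a further course.
- The number and percentage of retreated patients observed for the full 48 months, with conclusions on re-treatment safety limited to the span observed.

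If time without a TOPAZ infusion is shown alongside, split each retreated patient's time at the infusion date. Show time within 48 months of a prior-study course (the population in SAP 2.3.1.2) apart from time beyond it, since mixing them would blur the contrast. Label the comparison descriptive and non-randomised. Correct the cross-reference to the safety population in SAP 2.4.5 at the same time.

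The cost is SAP wording and a few tables. Infusion, onset and end-of-study dates are already needed for planned outputs, so no new data or visits are required. The downside is small numbers and wide intervals.
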